### 7.1. SUBJECT DISPOSITION AND WITHDRAWALS

Subject disposition will be summarized by presenting the number and percentage of subjects eligible for the study, treated with study medication and completed or discontinued from the study together with the primary reason for premature termination.

Major protocol deviations will be summarized for subjects in FAS.

A further summary table will be presented detailing the number of subjects in each analysis set. Furthermore, the number of subjects excluded from each analysis set will be summarized by reason for exclusion and will also be stratified by age groups.

All data will be summarized and listed.

#### 7.2. DEMOGRAPHIC AND OTHER BASELINE CHARACTERISTICS

Demographic (age, gender, height, weight, BMI and race) and baseline characteristics (e.g. child-bearing potential status, IgG trough level at screening, IgG trough level at baseline, IgG trough levels of specific antibody levels at baseline, IgG trough levels (subclasses 1-4)) will be presented in a summary table and a listing.

The summary table will be based on the FAS, PK Trough set, Specific IgG Trough PK set, Dense PK Subset and PPS, if applicable.

Age will be summarized as both a continuous variable and using the subgroup categories defined in Section 6.6.

All data will be listed.

Viral serology data (HIV, hepatitis B and hepatitis C) collected at screening (initial visit) will be listed only.

#### 7.3. MEDICAL HISTORY AND CONCOMITANT DISEASES

Medical history terms, including surgeries, will be coded using MedDRA version 19.0 to give a preferred term and a system organ class (SOC) term for each medical history term. At the end of the study, prior to database closure, medical history will be recoded applying the latest available MedDRA version available at this time point.

Medical history (previous and concomitant diseases) will be summarized by the number and percentage of subjects within each SOC and preferred term. This summary will be done overall and for each treatment schedule based on the FAS.

Medical history terms with ongoing ticked 'No' will be considered as previous diseases, with ongoing ticked 'Yes' as concomitant diseases.

All data will be summarized and listed.

#### 7.4. OTHER BASELINE CHARACTERISTICS

Previous established replacement therapy will be coded using the WHO Drug Dictionary (WHO-DD B3), March 2018. The number and percentage of subjects who used different established replacement therapies will be presented by A(natomical) T(herapeutical) C(hemical) Levels 2 and 4, and the investigator term.

Duration of the intake of an established replacement therapy with any IVIg reference preparation and with a single IVIg reference preparation will be summarized overall. The single IVIg reference preparation must have been at a constant dose that did not change by  $\pm 20\%$  of the mean dose, at regular dosage intervals.

Primary immunodeficiency disease history will be summarized by presenting the type of disease and time since disease diagnosis. Time since disease diagnosis will be presented by means of descriptive statistics. These summaries will also be stratified by age groups.

The summary table will be based on the FAS.

All data will be listed.

#### 7.5. MEDICATION

All medications will be coded using WHO Drug Dictionary (WHO-DD B3), March 2018.

The number and percentage of subjects taking previous and concomitant other medications (excluding immunoglobulins) will be summarized by ATC Levels 2 and 3.

The number and percentage of subjects taking premedications, to avoid AEs occurring in conjunction with the infusion of IVIg products during the study will also be summarized overall and for each treatment schedule by ATC Levels 2 and 3. These will be identified by a review of the coded medications and include antihistamines, antipyretics, and/or steroids with indication - prophylaxis.

The number and percentage of subjects taking previous and concomitant antibiotic medications will be summarized overall and for each treatment schedule by ATC Levels 2 and 3.

Concomitant antibiotic medication is one of the secondary efficacy endpoints and is described in the Section 8.2.5.

The number and percentage of subjects taking prohibited medication or treatment during the study will be summarized overall and for each treatment schedule by ATC Levels 2 and 3. Prohibited medication or treatment includes passive or active immunizations, administration of plasma preparations, or administration of other immunoglobulins and will be identified by a review of the coded medications.

The number and percentage of subjects taking rescue medication during the study will be summarized overall and for each treatment schedule by ATC Levels 2 and 3. Medication will be ticked as rescue medication by the investigator on the eCRF.

All presentations will be done based on the FAS.

#### 7.5.1. **Previous Medication**

Medications stopped prior to first infusion will be summarized as 'Previous' medications. Separate outputs will be generated for previous other medication, previous established replacement therapy (IVIg) and previous antibiotic medication (in addition stratified by route of administration). If subject has taken a previous medication more than once, the subject will be counted only once in the respective total (overall).

#### 7.5.2. Concomitant Medication

Medications taken at/after first infusion will be summarized as 'Concomitant' medications. Premedications taken to avoid AEs will be classified as concomitant medication, even if administered prior to the first BT595 infusion. Separate outputs will be generated for other concomitant medication, premedication, prohibited medication or treatment and rescue medication (added or changed concomitant medication due to the worsening of underlying disease). If subject has taken a concomitant medication more than once, the subject will be counted only once in the respective total (overall).
### 8. EFFICACY ANALYSIS

Efficacy endpoints are based on data from the eCRF. Data from subject paper diary and questionnaires are transferred into the eCRF.

The summary statistics will be based on the FAS and will be done by treatment schedule (3- or 4- week) and overall, if not stated otherwise.

In addition, all efficacy endpoints will be summarized descriptively stratified by age categories, gender, race and region as defined in Section 6.6. Age classes will be presented separately by FDA and by EMA criteria. The pediatric population (young children, children and adolescents) will be presented as a subtotal.

The primary efficacy endpoint, the number and type of acute serious bacterial infections, is determined through review of data collected on infections. Infections are reported as AEs which are obtained by the investigator through observation of the subject (including examinations and investigations), from any information volunteered by the subject, and through active guestioning. Subject diaries are reviewed to check for instances where the AE occurs and the subject is not on a site visit. If a subject suspects they have an infection between visits, the subject must inform the investigator as soon as possible. If the investigator confirms/suspects the subject has an infection, the subject must attend the site to be examined by the investigator. Subjects are instructed to bring their subject diary to each study visit. During each scheduled visit, subjects are asked about AEs occurring since their last visit and subject diaries are collected and reviewed for any signs of AEs (infections) occurring between visits before IMP administration. Specific diagnostic criteria, as recommended by the FDA guidance (Food and Drug Administration (FDA) Guidance for Industry: Safety, efficacy, and pharmacokinetic studies to support marketing of immune globulin intravenous (human) as replacement therapy for primary humoral immunodeficiency. June 2008), are used by the investigator to define each type of serious infection included in the primary efficacy analysis.

In addition to the primary efficacy endpoint, the following secondary efficacy parameters will be determined by the review of diary data: any infections, nonserious infections, time to resolution of infections, antibiotic treatment, number of days a subject was not able to attend school or work due to the infection and the treatment of the infection, information regarding hospitalization and fever episodes.

Immunoglobulin G trough level (total IgG) data are collected before each infusion and are recorded on the eCRF. An additional sample is taken after first BT595 infusion. The subject's total IgG trough levels are assessed at the local laboratory. The subject's total IgG trough level results from the previous infusion are made available to the investigator before the next infusion to allow dose adjustment if a subject's trough levels fall below 5 g/L.

Health-related quality-of-life data will be considered as exploratory efficacy parameters. Health-related quality-of-life data are collected using 2 subject questionnaires: Peds QL™ [PedsQL™ Measurement Model] and EQ-5D™ [EuroQol Five Dimension Health Questionnaire, 2015]. For pediatric subjects, the questionnaires may be completed by proxy reports (i.e., by the subjects' parent[s] or legally acceptable representative).

All pediatric subjects complete the 23-Item Pediatric Quality of Life (Peds QLTM) Measurement Model (Version 4.0), consisting of developmentally appropriate forms for children aged 2 through 4 years, 5 through 7 years, 8 through 12 years, and 13 through 18 years, and includes both child self-reports and parent proxy-reports, with the exception of children aged 2 through 4 years where only the parent proxy-report is required. The developmentally appropriate form is selected based on the subject's age recorded at screening (initial visit). The person completing the parent proxy-report should be constant for the duration of the subject's study participation. The Peds QLTM Core Scales encompass the essential core domains for pediatric health-related quality-of-life measurement: physical functioning (8 items), emotional functioning (5 items), social functioning (5 items), and school functioning (5 items). In each domain, the person completing the form is provided with a list of things which might be a problem for the subject and asked to respond with 'how much of a problem' each one is (i.e., 0 if it is never a problem, 1 if it is almost never a problem, 2 if it is sometimes a problem, 3 if it is often a problem, and 4 if it is almost always a problem).

All adult subjects rate their quality of life by self-completing the EQ-5DTM Health Questionnaire (Version 1.0). The EQ-5DTM essentially consists of 2 pages: the EQ-5DTM descriptive system page and the EQ visual analog scale (EQ VAS) page. The EQ-5DTM descriptive system comprises the following 5 dimensions: mobility, self-care, usual activities, pain/discomfort, and anxiety/depression. Each EQ-5DTM dimension has 3 levels (EQ-5D-3LTM): no problems, some problems, extreme problems. The EQ-5DTM EQ VAS records the respondent's self-rated health on a vertical, visual analog scale where the endpoints are labeled 'Best imaginable health state' and 'Worst imaginable health state'.

In addition to the Peds QL™ Measurement Model, pediatric subjects rate their quality of life by completing the youth version of the EQ-5D™ (EQ-5D-Y™; child self-report or proxy-report). The EQ-5D-Y™ consists of the same 2 pages: the EQ-5D-Y™ descriptive system page and the EQ VAS page. The descriptive system comprises the same dimensions as the EQ-5D-3L™, but using child-friendly wording (mobility; looking after myself; doing usual activities; having pain or discomfort; and feeling worried, sad, or unhappy) and has 3 levels: no problems, some problems, and a lot of problems. The EQ VAS endpoints are labeled 'The best health you can imagine' and 'The worst health you can imagine'. A proxy version of the form is used for children aged 4 through 7 years. All other pediatric subjects (8 through 17 years) self-complete the EQ-5D-Y™.

(Note for the US only: The age group of adolescents for the US is restricted to 12 to <17 years and therefore only subjects 2 to <17 years can be enrolled into the group of pediatric subjects.)

#### 8.1. PRIMARY EFFICACY ENDPOINT AND ANALYSIS

#### 8.1.1. Primary Analysis of Primary Efficacy Endpoint

The primary efficacy endpoint is the rate of acute serious bacterial infections (i.e., the mean number of acute serious bacterial infections per subject-year) and will be based on the total of all of the following events as defined by the FDA: bacteremia or sepsis, bacterial meningitis, osteomyelitis/septic arthritis, bacterial pneumonia, and visceral abscess.

Serious bacterial infections are identified by the following criteria:

- Any AE leading to the following MedDRA PTs: sepsis, bacterial sepsis, bacteremia, meningitis bacterial, osteomyelitis bacterial, arthritis bacterial, pneumonia bacterial, abdominal abscess.

- All AEs leading to any other PT are reviewed by the sponsor for a possible relationship to the primary endpoint (e.g. AEs including one of the following words: bacteremia, sepsis, meningitis, osteomyelitis, arthritis, pneumonia, and abscess). Identified AEs possibly related to the primary endpoint are queried to the investigator to clarify if the AE fulfils the FDA criteria for acute serious bacterial infections. The investigator transfers his decision to the eCRF (AE term).

The date of onset of an episode of acute serious bacterial infections is the day the diagnosis made.

For each subject, the study duration (days) will be calculated as:

(date of last visit) – (date of first infusion) + 1

The number of subject years will be calculated by summing the total subject days and dividing by 365. An estimate of the acute serious bacterial infection rate for BT595 will be obtained by dividing the total number of acute serious bacterial infections by the total number of subject years.

Any intra-subjects correlations of acute serious bacterial infections are not considered to follow a conservative approach for the infection rates.

For the primary efficacy analysis, the acute serious bacterial infection rate for BT595 and the upper 1-sided 99% CI will be estimated by using a Poisson model accounting for the length of the observation period per subject.

A generalized linear model assuming the Poisson distribution for the number of acute serious bacterial infections with the logarithm as link function will be used. The Poisson model will include the natural logarithm of the length of the observation period in years as an offset to account for the (possibly) different lengths of the observation periods per subject.

To assess the primary outcome for efficacy, the null hypothesis of 1 or more acute serious bacterial infections per subject-year will be tested against the 1-sided alternative hypothesis of less than 1 acute serious bacterial infection per subject-year at the 1% level of statistical significance. This 1-sided hypothesis test will utilize the same Poisson model as used for the calculation of the upper confidence limit. Rejection of the null hypothesis of 1 or more acute serious bacterial infection per subject-year will result in the acceptance of the alternate hypothesis of less than 1 acute serious bacterial infection per subject-year.

The primary efficacy analysis will be tested overall, e.g., without separation by treatment schedule.

Frequency tables presenting the number of subjects with number of experienced serious infections (total and by kind of infection) will be presented.

In addition frequency tables presenting the number of subjects with number of experienced serious infections (total and by kind of infection) for the subgroup of subjects that did not receive treatment for the full period of time, either by missing an infusion or discontinuing the study, will be presented.

A description of each serious bacterial infection will be provided in respective section.

Rate of acute serious bacterial infection will also be compared to relevant historical data from previous PID studies with Intratect® (already marketed 10% IVIg from Biotest) and to available data from Bivigam® (a 10% IVIg, which was formerly developed by Biotest), as well as to available data from the literature. These data will be provided by Biotest by the time of the analyses. The comparison to literature and discussion thereof will be part of the CSR.

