10.9 Determination of Sample Size

A sample size of at least 50 subjects will ensure a power of at least 80% to reject the null hypothesis of an acute serious bacterial infection rate greater or equal to 1.0 by means of a 1-sided test and a Type 1 error of 0.01 assuming a true underlying rate of acute serious bacterial infections of 0.5 per year. Thus, about 70 subjects will be enrolled to account for drop-outs.

The sample size will be at least 50 evaluable male or female subjects (2-75 years, inclusive), including at least 20 pediatric subjects (i.e., children [2-11 years, inclusive] or adolescents [12-17 years, inclusive]). Pharmacokinetic investigations will be carried out in at least 20 adult subjects and in pediatric subjects (6-17 years, inclusive).

The above sample size number (to obtain at least 50 subject–years) and inclusion of at least 20 pediatric (i.e., children [2-11 years, inclusive] or adolescent [12-17 years, inclusive]) subjects with the age distribution representative of the patient population follows the advice provided by both the EMA guidelines (EMA/CHMP/BPWP/94033/2007 rev. 2, 2010) and the FDA guidelines (FDA, 2008).

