# 3.5. DETERMINATION OF SAMPLE SIZE

A minimum sample size of 50 evaluable subjects was considered sufficient to ensure a power of at least 80% to reject the null hypothesis of an acute serious bacterial infection rate greater or equal to 1.0 by means of a 1-sided test and a Type 1 error of 0.01 assuming a true underlying rate of acute serious bacterial infections of 0.5 per year. About 70 subjects will be enrolled (treated) to account for drop-outs.

The sample size contains at least 50 evaluable male or female subjects (2 to <76 years), including at least 20 pediatric subjects (i.e., young children [2 to <6 years], children [6 to <12 years] or adolescents [12 to < 17 resp. <18 years]) and at least 20 adult subjects.

According to FDA advice from January 12, 2017 for Pediatric Study Plan, age groups are defined as stated in the FDA 2016 guideline differently for the US: The age group of adolescents for the US is restricted to 12 to <17 years and therefore only subjects 2 to <17 years can be enrolled into the group of pediatric subjects (i.e., young children [2 to <6 years], children [6 to <12 years] or adolescents [12 to <17 years].

The above sample size number (to obtain at least 50 subject–years) and inclusion of at least 20 pediatric subjects with the age distribution representative of the subject population follows the advice provided by the EMA (EMA/CHMP/BPWP/94033/2007 rev. 2, 2010) and FDA (FDA, 2008) and FDA (FDA, 2016).

Full pharmacokinetic (PK) characterization at steady state is to be carried out in at least 20 adult subjects and all consenting pediatric subjects (EMA: 6 to <18 years; FDA: 6 to <17 years). Optional sparse sampling will be taken for young children (2 to <6 years).

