a Two of the following should be present to make the diagnosis of sepsis in adults: temperature >38°C oral/ > 39°C rectal or <36°C oral or < 37°C rectal; heart rate >90 beats/min; respiratory rate >20 breaths/min, or PaCO2 <32 mm Hg; WBC count >12,000/mm^3, <4,000/mm^3, or >10% immature (band) forms (Ref. 14). For pediatric subjects, we recommend you employ the definition of sepsis using age-specific criteria as recommended by the International Consensus Conference on Pediatric Sepsis (Ref. 15).

b Indwelling catheter- or vascular access device-related blood-borne infections are not included because evidence is lacking that these are preventable with IGIV replacement therapy. For subjects without indwelling catheters or vascular access devices, a single blood culture positive for a pathogenic organism will meet the diagnostic criteria for bacteremia. (Multiple blood cultures are typically obtained in cases of suspected bacteremia/sepsis, as per standard medical practice, and the finding of a single positive culture should prompt additional confirmatory cultures). Subjects meeting criteria for positive blood culture but without 2 or more of the sepsis criteria listed above will be classified as having bacteremia.

e A blood culture positive for growth of *Streptococcus pneumoniae*, *Neisseria meningitides*, or *Haemophilus influenzae*, in combination with CSF leukocytosis and/or decrease in CSF glucose, can serve to confirm the diagnosis of acute bacterial meningitis (Ref. 16).

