#### **Contains Nonbinding Recommendations**

#### Infection: Bacterial Pneumoniad

- Symptoms: productive cough/change in character of sputum, dyspnea or tachypnea, chills, chest pain, rigors, headache, fatigue, sweats, anorexia, myalgias
- Physical findings: rales; pulmonary consolidation as reflected by: dullness on percussion, bronchial breath sounds, egophony; fever >38°C oral or > 39°C rectal, or <36°C, hypothermia (temperature < 36°C oral or < 37°C rectal)

- Laboratory tests: leukocytosis, differential WBC count of >10% band neutrophils, leukopenia, hypoxemia ( $PaO_2 < 60 \text{ mm Hg}$  on room air), positive blood culture, Gram stain and culture of deep expectorated sputume, positive culture with or without positive Gram stain of transtracheal aspirate, pleural fluid culture, lung biopsy, bronchoscopy with bronchoalveolar lavage (BAL) or protected brush sampling,
- Imaging studies: Pulmonary infiltrate with consolidation on chest X-Ray (CXR) (new in comparison with baseline CXR)

Infection: Visceral Abscess

- Symptoms: abdominal pain, anorexia, weight loss, cough/pleuritic chest pain (hepatic abscess), rigors (seldom present)
- Physical findings: intermittent fevers (temperature >38°C oral or >39°C rectal), abdominal tenderness, palpable mass, hepatomegaly, jaundice
- Laboratory tests: positive Gram stain and/or culture from the infected site, with isolation of an appropriate pathogen, positive blood culture, leukocytosis with accompanying left shift, differential WBC count of >10% immature (band) neutrophils, elevated serum amylase concentration (pancreatic abscess), elevated alkaline phosphatase concentration (hepatic abscess) pyuria in renal abscess
- Imaging studies: typical findings on ultrasound, CT scan, MRI scan, or radionuclide scan

Note: Items in **bold** are considered essential diagnostic features.

Source: Food and Drug Administration Guidance for Industry: Safety, efficacy, and pharmacokinetic studies to support marketing of immune globulin intravenous (human) as replacement therapy for primary humoral immunodeficiency. June 2008. Available from: http://www.fda.gov/downloads/BiologicsBloodVaccines/GuidanceComplianceRegulatoryInformation/Guidances/Blood/ucm078526.pdf.

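### SAP 8.1.1 counts adverse events under eight listed preferred terms as primary-endpoint infections with no stated check against the FDA criteria that define the endpoint

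*SAP*

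**What the plan says.** SAP 4.1 and the opening of SAP 8.1.1 define the endpoint as five infection types meeting the FDA diagnostic criteria, reproduced in SAP Appendix 1. The introduction to SAP Section 8 says these criteria "are used by the investigator to define each type of serious infection included in the primary efficacy analysis"; protocol 9.1.2.1 says the same.

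SAP 8.1.1 then gives two routes by which events are identified:

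- **Listed terms:** "Any AE leading to the following MedDRA PTs: sepsis, bacterial sepsis, bacteremia, meningitis bacterial, osteomyelitis bacterial, arthritis bacterial, pneumonia bacterial, abdominal abscess". The bullet contains no further condition.
- **All other terms:** the sponsor reviews the event, partly by keyword. Possible endpoint events are "queried to the investigator to clarify if the AE fulfils the FDA criteria for acute serious bacterial infections". The investigator's decision is entered in the eCRF as the AE term.

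Three other places bear on this:

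- SAP Appendix 1, note b: "Indwelling catheter- or vascular access device-related blood-borne infections are not included because evidence is lacking".
- SAP Appendix 1, visceral abscess, names organ-specific sites: "elevated serum amylase concentration (pancreatic abscess), elevated alkaline phosphatase concentration (hepatic abscess) pyuria in renal abscess".
- SAP 4.2 defines a nonserious infection as one that does not fulfil the FDA criteria. Preferred terms play no part in that definition.

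**The concern.** The endpoint is a set of diagnostic criteria, but for the listed terms the counting rule is a dictionary code. A code such as 'sepsis' or 'bacteremia' does not show whether the infection was device-related, yet that fact decides whether the event qualifies. The terms closest to the endpoint are the ones with no stated check.

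For off-list events the check exists, but its result is stored in the AE term. The SAP does not say what happens when the accurate term, after confirmation, still codes off the list.

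This count is the only confirmatory result of an open-label, single-arm pivotal trial, and SAP 8.1.1 also sets the rate beside historical data. Two statisticians following 8.1.1 could reach different counts from the same database.

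**Working it through.** **1. The plan's own figure.** Inputs:

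- a test "by means of a 1-sided test and a Type 1 error of 0.01" (protocol 10.9);
- "the null hypothesis of 1 or more acute serious bacterial infections per subject-year will be tested" (SAP 8.1.1);
- "assuming a true underlying rate of acute serious bacterial infections of 0.5 per year" (SAP 3.5);
- at least 50 subject-years and power of at least 80% (SAP 3.5).

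Under the null, X ~ Poisson(1.0 × 50 = 50). The exact test passes at the largest c with P(X ≤ c | 50) ≤ 0.01:

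- P(X ≤ 33 | 50) = 0.0070
- P(X ≤ 34 | 50) = 0.0108

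So c = 33. Power at rate 0.5 is P(X ≤ 33 | 25) = 95.0%. The stated 80% is met; the exact test first reaches it at 32 subject-years.

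**2. Following events through the rule.**

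| Event | FDA criteria (Appendix 1) | SAP 8.1.1 | SAP 4.2 |
|---|---|---|---|
| Device-related bacteremia coded 'bacteremia' | Excluded by note b | SBI, no check stated | Nonserious |
| Hepatic, pancreatic or renal abscess, confirmed on query, term codes off the list | Qualifies | Found and queried; counting not stated | Not nonserious |

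The first row is a contradiction: one event falls in two categories meant to exclude each other. It assumes that the event codes to a listed term, and the documents do not describe the coding. The second row is a gap. The list has only 'abdominal abscess', while Appendix 1 names three organ sites.

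**3. Size of one event.** One event in 50 subject-years is 1/50 = 0.02 per year, or 4% of the assumed 0.5. Upper 99% limits at T = 50, with exact = χ²(0.99; 2(x+1))/(2T) and Wald = (x/T)·exp(2.326/√x):

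| Events x | Rate | Exact | Wald (log link) |
|---|---|---|---|
| 3 | 0.06 | 0.201 | 0.230 |
| 10 | 0.20 | 0.403 | 0.417 |
| 25 | 0.50 | 0.786 | 0.796 |
| 33 | 0.66 | 0.980 | 0.990 |
| 34 | 0.68 | 1.004 | 1.013 |

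The expected count under the plan is 0.5 × 50 = 25, which is 33 − 25 = 8 events inside the boundary. The Wald limit gives the same cut-off.

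**4. Range of misclassification.** The documents give no misclassification rate, so the percentages below are assumptions.

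- *Over-counting* (listed terms unchecked), true rate 0.5: power P(X ≤ 33 | 25k) is 87.2% at k = 1.1, 74.4% at k = 1.2 and 58.1% at k = 1.3.
- *Under-counting*, which applies only if the gap were resolved by leaving confirmed off-list events out, true rate 1.0: false success P(X ≤ 33 | 50s) is 1.7% at s = 0.95, 3.8% at s = 0.90 and 15.1% at s = 0.80, against 0.7% at full capture.

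**The case against.** The strongest reply is that the check is already assigned. SAP Section 8 and protocol 9.1.2.1 give the FDA criteria to the investigator for every serious infection type in the primary analysis. The protocol also requires objective findings, and it has the onset date and details of each SBI recorded in the eCRF. On this view a listed term has met the criteria before it is coded. That is a fair account of the intention, and it rules out reading the plan as one that never applies the FDA criteria; the off-list route also applies them explicitly. It does not close the gap. The operative rule in 8.1.1 counts on the code, and no stated step reconciles a listed-term event with the investigator's assessment. The promised description of each SBI covers events already identified. The eCRF itself is not in the documents, so one cannot say that it lacks an SBI field, only that 8.1.1 does not count from one.

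A reader might infer that confirmed hepatic, pancreatic or renal abscesses are lost, or must be given a less accurate diagnosis to count. The documents do not support this. The second route exists for terms off the list, and 'abscess' is one of its keywords, so such an event is found and queried. Nothing requires it to be recoded to a listed term. What stands is that the SAP does not say how it is then counted.

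A reader might also cite a sepsis without a positive culture as a non-qualifying event that would count. Appendix 1 marks essential features in bold, which the text available here does not show, and note a defines adult sepsis by clinical and laboratory signs. That example cannot be established; the device exclusion in note b can.

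Finally, the contradiction on listed terms can only add events. It therefore costs power and does not inflate the type I error. This is correct, and it limits the severity.

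**Conclusion.** The point holds and should be fixed. As written, SAP 8.1.1 can count a listed-term event that the endpoint definition excludes and that SAP 4.2 calls nonserious. It also leaves open how a confirmed off-list event enters the count. The first fault is conservative. The second has no known direction until the rule is written, and would be anti-conservative only if such events were left out.

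A reader might infer from the arithmetic that two or three misclassified events threaten the result. They do so only near 33 events per 50 subject-years; elsewhere they change the reported rate and the historical comparison but not the conclusion. The sample size stands. These statements assume exactly 50 subject-years. About 70 subjects are to be enrolled, so exposure may be larger and the cut-off higher.

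**What to change.** Amend SAP 8.1.1 as follows:

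- Use the eight preferred terms and the keyword search only to find candidate events.
- For every candidate, listed terms included, have the investigator record in a dedicated eCRF field or query: FDA criteria met (yes/no), which of the five SBI types, and whether the device exclusion in Appendix 1 note b applies.
- Count the primary endpoint from that record, whatever the preferred term.
- Leave the AE term as the medically accurate diagnosis.
- Confirm the final list of events at the data review meeting before database lock.

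The cost is a short SAP change and a few extra queries through a process that already exists. There is one downside. SAP Final 2.0 is dated 24 April 2020, after the planned last visit of November 2019. Re-checking listed-term events that late in an open-label trial can only remove events, which favours the sponsor. The count and upper limit under the present preferred-term rule should therefore also be reported as a sensitivity analysis, with each removed event listed and the reason given.
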